8.13. No-Show Protocol

If enrolled participants are not available for a session (despite attending the medical visit), we will attempt to contact non-enrolled participants in a number of ways.

Participants who “no show” for a scheduled session will first be called or texted at 15 minutes past the appointment time. The staff member should contact the participant to check on him/her and attempt to reschedule the appointment (i.e., leaving a message to this effect if the participant does not answer the phone). If the participant is not contacted the day of the appointment, the interventionist should also follow-up with the participant the next day in an attempt to reschedule. Alternate contact info may also be utilized in efforts to reach the participant.

8.13.1. Rescheduling Protocol

Participants will be allowed unlimited occasions of rescheduling a session , as we want to retain all enrolled participants in the study. However, staff (together with the Project Coordinator) should use their judgment about this rule on a case-by-case basis and

always prioritize completing assessments if the participant cannot complete intervention sessions.

8.13.2. “Hard to Reach” Participant Retention

Participants who miss sessions and remain in session window should be subject to intensive retention efforts by Interventionists.

Main strategy: Starting with preferred modality, cycle through different modalities, days of the week, times of day, and different strategies to reach participant.

Modalities: phone, text, email, mail, alternate contact

Phone call strategies:

Call and leave a voicemail

Call once then follow up with text (ex: Hi _____, I just left you a message trying to reschedule, if you can call me back when you get a chance that would be great!)

Call once, then call again 10-15 minutes later (try leaving a VM the first time, but if they don't answer the second time don't leave another message)

Call with google voice number or clinic telephone to catch participant off-guard

Call alternate, ask if they know a good time to call participant or if you can leave a message with them (do not disclose the purpose of the study to alternate)

Alternating times of day within a week

For those who are early or middle of their window, try one morning call, one afternoon call, and one evening call within the span of a week

Ex: Monday afternoon, Tuesday morning, Thursday evening

Can also send texts or other modalities during this time

E-mail and Mailing strategies:

For participant who you've had a hard time reaching via quicker methods

Examples:

Hope you're doing well! We've had a hard time getting a hold of you by phone so I just wanted to check in. If you could give me a call at [contact], we'd love to get you scheduled for you next session!

Just wanted to check in on you because I've had a hard time getting a hold of you. The last day for you to do this session is _____. If you can give me a call at [contact], we can figure out a time that works for us to get this session in!

Facebook Message Strategies:

We will have links stored for participants who message us on Facebook. This will allow us to send a message to those participants from the SMART page.

Use the same type of language used in mailings and/or text messages

Example

Hope you're doing well! We've had a hard time getting a hold of you by phone so I just wanted to check in. You can either message me back on here or give me a call at [contact].

Just wanted to check in on you because I've had a hard time getting a hold of you. The last day for you to do this session is _____. Would you have some time Tuesday at 9 to do your session?

Also a great tool to get updated contact information if needed

Contact attempts per stage in window:

Early to mid window: contact at least 3 times a week using at least 2 different modalities

Late window (last week): contact daily at different times of the day, leave message with last day to do session so the participant has a deadline.

As a last chance effort the day before a window closes, you could text the participant and offer them a slot the next day. You can tentatively book them on the calendar and even if they don't respond, go ahead and try to call at the suggested time.

Ex: Hi _____, tomorrow's our last day for us to get this session in. Could I call you at 10:00 tomorrow to do that?

Should the window for a session close, retention efforts should be stopped, but resumed just prior to the opening of a new window.

18.13.3. Participant Withdrawal

Some participants may passively drop out of treatment, whether because of scheduling conflicts, life stressors, disappointment with their outcome, or not liking the phone sessions. Some participants will develop conflicts or barriers that keep them from

attending phone sessions on a regular basis and may wish to actively withdraw from the study.

These participants may or may not be aware that there are options to help them stay involved.

For participants who decline all offers of intervention, be sure to leave the door wide open.

If the participant is reached, the Interventionist will attempt to re-engage the participant with any of the following techniques:

Maybe we can change something?

Discuss the barriers with the participant. Help the participant brainstorm solutions to the barriers or any alternative options that will help the participant stay involved.

Offer flexible schedules for participating in phone sessions. Can they participate in just two meetings a month? One meeting a month? Can they take a break for a month or two and then see if they can resume phone sessions? Stick to just email communication for a period of time?

The Project Coordinator may also contact the participant to see if switching counselors would help the participant re-engage.

Document all efforts to keep the participant enrolled in the study on the Contact Notes.

Maybe you will want to start again at the next session ?

Maybe the participant could take a break from the study (become inactive), and possibly resume later if there are later visits that could be completed (ex: a participant cannot complete S1 but they might want to be contacted at S2). Make sure they are aware that you are available to help them with questions or concerns at any time and that we may periodically contact them throughout the remainder of the study. Interventionists should indicate that they would be happy to work with a participant anytime they are ready to focus again on smoking cessation.

Can you still participate in the last follow up?

If the participant does not want to continue participating in phone sessions, emphasize to them the importance of completing the assessments. Ask the participant if he/she is willing to complete these measures. The participant would be considered inactive and would still receive the \$50 gift card if the session is completed (S1, S2, S3, or S4). Emphasize that their data is needed for the success of the research, whether or not they have been actively participating or not and whether or not they've quit. In order to answer the research questions, we need to know what worked and what DID NOT work for

participants so we can help others better in the future. Explain that without their data, we will be missing some of the most crucial information we need to collect.

Participants who do not complete the Baseline assessment within the designated window will be administratively withdrawn from the study since they did not complete any treatment.

18.14. Official Withdrawal Procedures

Document all efforts to keep the participant enrolled in the study on the Contact Notes.

If, after all alternative options are explored and exhausted, the participant still chooses to withdraw from the study, document the date of the discussion.

The Study Coordinator will put notification of intent to withdraw in writing in a letter to the participant.

A copy of an official withdrawal letter is provided in Appendix B.

Study Coordinator will then:

Mark as withdrawn on the Regulatory Form.

Report to IRB on annual progress report.

Notify PI by email if there are abnormal circumstances surrounding the withdrawal.

9. Data Safety Monitoring Board

9.2 Responsibilities of the DSMB

The roster of proposed DSMB members will be submitted to NCCIH prior to initiating recruitment (see DSMB Charter, separate document due to length). Types of credentials that our intended DSMB members will possess are: 1) experience conducting behavioral intervention studies; 2) experience with treating opioid use disorder; and/or 3) biostatistical expertise in intervention studies. As DSMB members, they will review the reports sent by the study statistician (at the frequency outlined above) and will use the checklist attached to this document (Appendix C) to determine whether there is any corrective action, trigger of an ad hoc review, or stopping rule violation that should be communicated to the study investigator, the University of Tennessee Health Science Center IRB and the NCCIH.

10. ALTERNATIVE PROCEDURES: COVID

In the case that study staff are unable to recruit and provide the intervention in-person, the following alternative procedures will take place.

All individuals entering the CAS must abide by the rule of wearing a face mask at all times.

Procedures

Recruitment

Study staff will review the clinic schedule the day before and the day of to determine which patients are eligible. Study staff will come into the clinic to discuss the study and recruit eligible patients.

Enrollment

Consent

If the patient agrees to participate, the study staff will consent in person. The study team will take all precautions to protect themselves and the patient (e.g., PPE and practice social distancing).

For participants unable to complete consent in person and who have access to a computer, a DocuSign link will be sent immediately to conduct consent during the call. A blank copy of the consent form will be mailed to the participant

All other consent procedures will be the same as written above.

Randomization

Once the patient consents and completes baseline assessments, randomization procedures will stay the same as written above.

Baseline Assessment

Baseline assessment will take place in-person or over the telephone. Assessment must be completed prior to the participant's first physician return visit. Procedure will stay the same as written above.

Sessions 1-4

Following the Baseline Visit (BV), participants will complete sessions on the same schedule as their appointments at CAS, but windows will not exceed 30-day increments. Sessions and follow-up procedures will stay the same as written above with a few modifications (see below).

CM Session

Study staff will contact participants by phone or text to schedule a time to complete their assessment and CM intervention via Zoom call on the day of the participants' scheduled appointment. The participant will be given a 30-day window (starting with the day of their office visit) to complete the assessment or it must be completed prior to the next scheduled clinic visit for the patient.

If participant attends the physician appointment **and** has buprenorphine in urine:

Once the assessment is complete, the study staff will spin the number wheel while the participant is on the phone ("virtual wheel"). The study staff will inform the participant of the gift card amount earned and will immediately mail the gift card.

Study staff will also take a screenshot of the number wheel results, and text or email the participant the photo. The study staff will upload the photo to FileMaker for future records.

For those who **DO NOT** have buprenorphine in urine:

Once the assessment is complete, the study staff will inform the participant that they did not have buprenorphine in their urine and are not eligible for the virtual spin.

BSM Session

Study staff will contact participants by phone or text to schedule a time to complete their assessment and intervention via Zoom call. The call will be scheduled and completed within 30-days or the day before their next scheduled office visit. The intervention portion will be audio recorded.

Recording procedures will be the same as written above.

Incentives

Gift Card Distribution Procedures

Procedures will stay the same as written above with slight modifications. Gift cards will be mailed. A google sheet will be used to track the gift cards distributed.

Virtual mailing procedures in section 14.

Gift Card Storage

All procedures will stay the same as written above.

11. PROFESSIONALISM IN THE WORKPLACE

Employees will follow University of Tennessee Policies, some of which are noted in this section.

11.1. Professional Attire

It is important that employees maintain a conservative, neat and clean appearance appropriate for the work environment. Preventive Medicine takes a “business casual” approach which includes suits, dress pants, dresses, and skirts, but may also include collared shirts, golf or “polo” shirts and pressed khaki pants.

Attire that is not appropriate for the workplace includes t-shirts, tight or short pants/skirts, tank tops, halter tops, low-cut blouses or sweaters, or any extreme style or fashion in dress, footwear, accessories, or fragrances. Certain employees may be required to meet special dress, grooming and hygiene standards, such as wearing uniforms or protective clothing, depending on the nature of their job, which will be defined by the department. Some departments adopt casual or dress-down days. In this instance employees are still expected to adhere to the aforementioned appearance but are not permitted to wear ripped, frayed clothing, disheveled clothing, work-out gear, tight clothing, revealing or otherwise workplace-inappropriate clothing is not permitted on any given day.

11.2. Professional Behavior

11.2.1 Respect for Others

People are the University of Tennessee's most important resource for accomplishing its teaching, research, and public service missions. Accordingly, employees are expected to be committed to creating an environment that promotes academic freedom, diversity, fair treatment, and respect for others. Employees are expected to treat one another public in an honest and respectful manner. Specific examples of this behavior include disorderly conduct, including, but not limited to, using discriminatory, abusive, or threatening language; fighting, provoking a fight, or attempting bodily harm or injury to another employee or to any other individual or threatening physical action or injury on university property or during university activities; or other conduct that threatens or endangers the health, safety, or well-being of any person.

11.2.2 Responsible Use of University Resources

Employees must use university property, funds, technology, time, and other resources for legitimate business purposes. Employees must not use university resources for personal gain or to benefit third parties. These could include using university resources for personal needs, family matters, schoolwork, or abusing work time for any personal reasons. This also includes instigating or participating in deliberate low productivity and/or interfering with another employee's work.

11.2.3 Standards of Attendance and Timeliness

SMART Project 3 employees are expected to be on time for work and on time for sessions. Employees should be clocked in and at their desk at their start time at the beginning of the day. Please note: Remote work still requires employee engagement during working hours, as designated.

The university has policies on repeated tardiness and absences. Repeated tardiness is defined as arriving at work past the appointed starting time without supervisory approval. Other absences include the failure of employees to report to their work place at the beginning of the work period, leaving work before the end of the work period, and failure to inform the supervisor when leaving the work area.

All appointments with participants should be started at the exact time scheduled, give or take 1 minute. If a staff member knows they will be more than 15 minutes late for a scheduled appointment, they should ask another staff member to call the participant and inform them that they are running late or to call and reschedule the participant.

12. MEASURES

12.1. Table 1. List of Measures

Measure	Time to Complete (minutes)	Baseline	1,2, 4, and 8 week sessions	8 week blind	Medical Chart at 30 days
Contact Information	1	X			
Referral source (how did they get to the CAS)?	<1	X			
Screening Questionnaire	<1	X			
Exclusion reason (if applicable)	n/a				
Demographics (gender/race/ethnicity/education/zip code/insurance)	3	X			
Opioid Use Disorder (Diagnostic and Statistical Manual of Mental Disorders-5) ⁹³ interview	1	X			
Attended first physician visit	n/a		X		
Attended second physician visit	n/a		X		
Attended third physician visit	n/a		X		
Attended fourth physician visit	n/a		X		
Number of treatment visits attended (allow for drop out, drop back in): CUMULATIVE ADHERENCE	n/a				X
Urine Toxicology (buprenorphine and all other substances)	n/a	X	X		X
Timeline followback on alcohol, substance use, and opioid use	3	X	X		
Delay Discounting ⁵⁸	2	X		X	
Opioid Purchase Task ⁴⁶	1	X	X		
Engagement in Substance Free Activities ⁵⁴	2	X		X	
Time Spent On Activities	2	X			
Opioid Craving Symptoms ⁹⁵ (Opioid Cravings Scale)	1	X	X		
Buprenorphine-Naloxone dose log (did you miss any days?)	<1		X		
Dosage of Buprenorphine-Naloxone Prescribed (obtained from medical record at each session)	n/a	X	X		X
Treatment Satisfaction	4			X	
Prescription Drug Monitoring data	n/a	X	X		X
PEG for Chronic pain (3 items)	<1	X	X		
EQ5D5L (6 items) Quality of life for cost-effectiveness analyses	3	X		X	
PHQ-2 depression 2 items	<1	X	X		
GAD 2 anxiety 2 items only (also a 7 item version)	<1	X	X		
Treatment history (times in treatment, medication used)	<1	X			
Economy Contribution (3 items)	<1	X	X		
If dropped out: Are you receiving but (or opioid replacement) treatment somewhere else?	<1		X		
Adverse Events	<1		X		
Participant time to complete all measures at sessions:		20.5	11	10	n/a

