3.4.3. Final Assessment (Participant)

All participants will complete a blinded treatment satisfaction follow-up assessment shortly after completing Session 4 Part 1. Session 4 Part 2 assessment is to be conducted by an assessor blind to study conditions.

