8.6. Intervention Sessions

Prior to the session, Interventionists will prepare for the brief assessment conducted during each treatment session by finding the participant in the Filemaker database, or if offline, entering the participant information on the top of the assessment materials.

Interventionists will also prepare to administer the appropriate session (1, 2, 3, or 4) (within the appropriate condition).

In addition, Interventionists will prepare the recording device to ensure that the session is recorded. If remote, the interventionist will text or email the participant a Zoom telephone number with a meeting ID for them to call and be placed in a meeting. The interventionist will ensure that Zoom is recording once permission is granted from participant. All sessions will be recorded and uploaded to OneDrive folder (SMART Project 3/Recordings) and labeled with the participant's study ID, session number (1, 2, 3, 4), condition (CM vs. BSM), and staff initials. (e.g. 301 S2 BSM AB)

At each session , the Interventionist will meet with the participant to complete the assessment questionnaires and complete the intervention – either a BSM session or a wheel spin for additional gift cards for CM (if requirements are met).

If the participant drops out of treatment at the Center for Addiction Science, they will no longer receive the CM or BSM. However, all assessments will be conducted regardless of the participant's adherence to medical treatment at the CAS. Upon completion of the assessment, participants will still earn the \$50 gift card. This will allow us to understand the reason for the participant's non-adherence to treatment, and to evaluate whether these individuals pursue treatment elsewhere.

The intervention scripts are available in section 13 of the manual of procedures.

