8.5.2. BSM Intervention Description

Record all interactions with BSM participants.

Participants who are assigned to BSM will complete their assessments with the interventionist. After the assessments are complete, the interventionist will engage the participant in the BSM intervention. A SOBER handout will be given to the participant at their baseline visit (*See section 13*). Participants will also receive a Tips for Improving Self-Control handout at session 4.

If a participant misses a session, the interventionist will continue with the next session in numerical order. So, if a participant is on S2 and missed S1, the interventionist will deliver S1 content during session 2.

This intervention consists of 4 sessions:

Session 1

This session will cover reasons for attending treatment, goals, time spent on valued activities, future events, and mindfulness-based coping (SOBER).

Session 2

This session will substance goals check in, substance free activities, and mindfulness-based coping (SOBER).

Session 3

This session will cover goals check in, substance free activities check in, and mindfulness-based coping (SOBER).

Session 4

This session will cover self-control improvement, and review goals, substance free activities, and mindfulness-based coping (SOBER).

In the event that a participant misses their clinic visit, assessments may still be completed at any time during the window. If the participant completes their clinic visit **before the session window closes** they may be contacted to complete a counseling session.

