13. BSM INTERVENTION SCRIPT

Psychosocial Intervention Session 1 (40 minutes with assessments):

Session Prep:

- a. Ensure participant has received SOBER Handout at baseline
- b. Print off blank Goals worksheet for Session 1 to fill out during session
- c. Participant should have completed the “Time Spent on Activities Worksheet” at baseline.
 - i. Have a graph of the time spent in each activity prepared and sent to the participant before the session begins
- d. Print off blank Future Event Description worksheet for Session 1 (Goals, Future Event Description) to fill out during session

1. Introduction (2 minutes)

a. Getting Permission to Record

- i. *Hi _____, is this still a good time for us to do our first session together? Great!*
- ii. *Before we get started today, I wanted to let you know all of our sessions will be recorded for the purpose of the study.*
- iii. *Do I have your permission to record this session? Thank you so much.*

b. Mandated reporting

- i. *Also, I wanted to let you know that I am a mandated reporter. That means if you let me know about any ongoing abuse, either to yourself or to someone else, or if you inform me of any intentions to harm yourself or someone else, I am obligated by law to report that. If anything like that comes up during any of our sessions, I would let you know ahead of time.*
- ii. *Do you have any questions about that?*

2. Assessment (10 minutes)

- a. Complete session one assessment forms in FileMaker.
- b. *Thank you for taking the time to answer all those questions.*
- c. *Because you finished your assessment, I will mail you that \$25 gift card. Do you prefer Kroger or Walmart? Great!*
- d. *Please allow 2-3 business days for it to arrive. If there are any issues, please don't hesitate to reach out!*

3. Build Rapport (1 minutes)

- a. *So I'd like to get to know a little more about who you are. Tell me who are the most important people in your life and one or two things you like to do – just a minute's worth of who you are.*
 - i. Wait for participant to tell you about themselves – MAXIMUM 1 minute

4. Orientation to Session (1 minute)

- a. *Thank you for telling me about yourself.*
- b. *Let me tell you about what we will be doing with our time together.*
 - i. *My overall goal is to support your treatment at the Center for Addiction Science and help you meet your goals.*

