 4. **Expand:** Work to expand your awareness of the situation. You already are slowing down your breath, now focus on the breath to allow your body and your mind to soften. We are expanding our awareness back out to the feelings in the body, the sensations of being in the room, and allowing ourselves to be centered and grounded in this moment.
 5. **Respond:** Allow yourself to respond mindfully. How can you truly take care of yourself in this situation? What do you really need? Take a moment to choose your response – knowing that you do have a choice.
 - a. People may think of this as “wise mind” – acting with purpose and reason.
 - b. Importantly, the person might still choose the same reaction/response – that is okay. Our goal is to just be more present with our response to situations, triggers, urges. Allow the participant some time to process this part of SOBER. Encourage the participant to be empowered to make a choice and to be more present when choosing a response.

7. Wrap-Up (2 minutes)

- a. *We covered a lot today during our session. I did want to remind you that next time is actually going to be our last session together! Do you have any questions for me today?*
- b. *Let's schedule our final session together.*
- c. Provide participant with date and time of session.

Psychosocial Intervention Session 4 (38 minutes with assessments):

1. Introduction (1 minute)
 - a. Getting Permission to Record
 - b. *Hi _____, how are you today? Is this still a good time for us to do our final session together? Great! And before we get started today, do I have your permission to record this session? Wonderful, thank you!*
2. Assessment (20 minutes)
 - a. Complete session four assessment forms in FileMaker.
 - b. *Because you finished your assessment, I will mail you that \$25 gift card. Do you prefer Kroger or Walmart? Please allow 2-3 business days for it to arrive.*
 - c. *Thanks for getting the assessment completed today.*
3. Orientation to Session (1 minute)
 - a. *Today, we will discuss improving self-control. We'll also review the opioid-free activities you've been trying, and touch base on how SOBER has been working for you.*
 - b. *What questions or thoughts do you have for me before we get started?*
 - c. If the participant missed the previous session , take a few moments to inform them of the information they missed.
4. Improving Self-Control (5 minutes)
 - a. *I would like to introduce you to an activity we call "improving self-control."*

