Statistical Analysis Plan: SMART Project 3 (Efficacy Study)

Because these analyses will focus on determining and intervention feasibility and satisfaction, and preliminary intervention effect sizes (with less concern focused on testing for statistical significance), outcome analyses will be conducted using a separate analysis for each outcome at each follow up observation. To compare groups, baseline and follow up variables will be entered into a 5 (baseline vs. follow ups at 1, 2, 3, and 4 weeks) by 2 (CM vs. BSM) analysis of variance (ANOVA) which will yield effect sizes for time, and interactions of time by intervention. The primary dependent variables will be attendance at physician visits, saliva drug screen data (positive for buprenorphine and negative for illicit opioids), and prescription drug monitoring. We hypothesize that a greater number of CM participants will demonstrate adherence to buprenorphine-naloxone than BSM, but that those randomized to BSM will report increased time allocated to substance-free activities, decreased delayed reward discounting, and demand for opioid.

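### After randomization, opioid demand is measured only by the unblinded interventionist and before each day's content; no value is blinded or follows Session 4, unlike delay discounting in the same hypothesis

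*Protocol*

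**What the plan says.** The SAP's closing hypothesis is directional. It expects more adherence under CM, and under BSM more time in substance-free activities together with "decreased delayed reward discounting, and demand for opioid".

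Table 1 (Protocol 12.1) is the only itemised schedule. Its row for the one demand measure reads "Opioid Purchase Task ⁴⁶ 1 X X": one minute, marked at baseline and at the sessions. The delay discounting row reads "Delay Discounting ⁵⁸ 2 X X": two minutes, where the second mark belongs to the 8-week blind column and the sessions column is empty.

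On who asks the questions, 8.6 (Intervention Sessions) states that "the Interventionist will meet with the participant to complete the assessment questionnaires and complete the intervention". Section 4.3.4 has the same staff deliver both interventions. The exception is the end of treatment, where 3.4.3 says "Session 4 Part 2 assessment is to be conducted by an assessor blind to study conditions".

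On order, 8.5.2 says "After the assessments are complete, the interventionist will engage the participant in the BSM intervention". The section 13 scripts agree. In Session 1, "Complete session one assessment forms in FileMaker" is part of the second of nine steps; in Session 4, "Complete session four assessment forms in FileMaker" is part of the second of seven. The Session 2 and 3 scripts also put assessment second, and 3.6.2 lists assessment before intervention for both arms.

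**The concern.** Two mechanisms are named in one hypothesis and measured under different conditions. Delay discounting is taken once after randomization, by a blinded assessor, after Session 4. Opioid demand is taken four times after randomization, always by someone who knows the arm, and never after the fourth session.

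The task (12.2.15) is hypothetical self-report: how many pills the person would buy at each price. From Session 2 on, a BSM participant gives that answer to the counselor who has already worked with them on goals, relapse and recovery. If this shifts answers at all, the likely direction is toward lower reported demand under BSM, which is the direction hypothesised. The timing pulls the other way, because a real BSM effect has not had the whole course in which to appear. The SAP's stated purpose is preliminary effect sizes, so what is at stake is how well the demand effect size can be interpreted and compared with the one for discounting.

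**Working it through.** There is no stated figure to reproduce. The check compares the Table 1 columns with the order of events and then does simple counts.

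**1. Exposure before each demand value, for a participant who attends every session.** Assessment precedes intervention at each session (3.6.2, 8.5.1, 8.5.2, section 13).

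| Value | Sessions already received | Who administers |
|---|---|---|
| Baseline | 0 of 4 | before randomization (8.2.3); paper or staff interview (8.2.2) |
| Session 1 | 0 of 4 | interventionist |
| Session 2 | 1 of 4 | interventionist |
| Session 3 | 2 of 4 | interventionist |
| Session 4 | 3 of 4 | interventionist |
| Blind call (Session 4 Part 2) | 4 of 4 | blinded assistant; demand not scheduled |

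The counts are the same in CM, where the wheel also comes after the assessment (8.5.1). By Session 1 a BSM participant has had only the SOBER handout. The 30-day step (3.4.4, 3.6.4) is chart review and adds no demand value.

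**2. Share of scripted BSM before the Session 4 value.** Session totals and assessment minutes are from section 13.

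- Session 1: 40 − 10 = 30
- Session 2: 39 − 10 = 29
- Session 3: 41 − 10 = 31
- Session 4: 38 − 20 = 18
- Total: 30 + 29 + 31 + 18 = 108
- Before the Session 4 task: 30 + 29 + 31 = 90, and 90/108 = 83%

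Counted by sessions instead of minutes, the share is 3/4 = 75%. The minutes are the better guide to content, because Session 4 is mostly review; its one new topic is five minutes on self-control.

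**3. Room in the blind call.** The items marked in that column of Table 1 are delay discounting 2, substance-free activities 2, satisfaction 4 and EQ-5D-5L 3: 2 + 2 + 4 + 3 = 11 minutes. Table 1 prints 10, and 3.6.3 allows 25. With the one-minute task the listed items come to 12.

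**The case against.** The best defence is that the design is reasonable for a secondary mechanism in a pilot of 40. Measuring before each session captures carry-over since the previous one and avoids an immediate response to counseling. The order is the same in both arms. Session assessments continue even for people who leave treatment (8.6), so they are less exposed to dropout than one late call. The protocol's primary outcomes (3.3) and the SAP's primary dependent variables do not include demand. All of this stands, and it is why the session values should stay in the analysis.

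It can also be said that 3.6.3 and section 14 mention Part 2 assessments without listing them, so the task might already be included. That lowers certainty a little, but Table 1 is the only itemised list and leaves the task out.

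Blinding has limits too. Participants know their arm (8.2.3), and the assistant also has retention, data-abstraction and data-checking duties (4.3.5, 8.8.1). A blinded caller still separates the answer from the counseling relationship.

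Some stronger readings are tempting but not supported:

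- *That demand is never measured free of knowledge of the arm.* The baseline value precedes randomization.
- *That CM contact is only a two-minute wheel.* CM participants also complete about ten minutes of assessment with the interventionist at each session (3.4.1), and every participant has an assigned counselor (8.2.3).
- *That averaging the four session values would show only a small part of the full effect.* The SAP plans no such average. It describes an analysis at each follow-up and a time-by-intervention term.

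**Conclusion.** The point holds for values after randomization. All four are unblinded, the first precedes any intervention session, and none follows Session 4. The SAP's 5 by 2 analysis nevertheless treats the Session 1 value as a follow-up.

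The shortfall in exposure at Session 4 is modest: about 17% of scripted BSM minutes (18 of 108) are still to come. This assumes full attendance and delivery to the scripted times. Under 8.5.2, content missed at one session is delivered at the next, so a participant who misses sessions will have received less.

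The size of any reporting bias is unknown, and the documents give nothing from which to estimate it. A reader might infer that the demand effect size is therefore uninterpretable. That goes too far: the session values remain usable as unblinded, pre-session measurements. What is missing is a blinded value after the full course to set beside them and beside delay discounting. Because demand is not a primary outcome, this is a worthwhile low-cost change and does not undermine the trial's conclusions.

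**What to change.** In Table 1, mark the Opioid Purchase Task in the 8-week blind column, to be given by the blinded research assistant before the satisfaction survey, whose answers could reveal the arm.

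In the SAP, add that the baseline-adjusted difference between arms at this blind value, taken after Session 4, will be reported alongside the planned session analyses, and that Session 1 values will be labelled as preceding any intervention session.

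The cost is one more minute in a call that already takes place with an existing assessor, one more repeat of the task, and a sentence or two in the SAP. The new value will be missing for participants who do not complete Part 2, which section 14 schedules only after Part 1 and the intervention. For those who left treatment early but still take the call, it will not reflect a full course. The session values stay in the analysis to cover participants without the blind value.
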